4.2 Secondary Objectives

[figure not shown]
- To evaluate the effect of injection-to-meal timings (immediately before the start of meal, and 20 minutes following the start of the meal) on the GD response to LY900014 compared to Humalog, as measured by the mixed meal tolerance test (MMTT).
- To evaluate the tolerability of LY900014.

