7. SAMPLE SIZE JUSTIFICATION

An initial 36 patients may be enrolled in order that approximately 30 patients complete the study. Thirty completing patients will provide greater than 95% power to demonstrate a 2-fold increase in the serum insulin lispro area under the concentration versus time curve from time zero to 30 minutes [AUC(0-30min)] between LY900014 and the Humalog. Testing will be done at an alpha level of 0.05 with a 2-sided confidence interval (CI). The sample size will also provide greater than 95% power to demonstrate a 35% reduction of early 50% time to maximum observed drug concentration (early 50% t_{max}). The estimated standard deviation (SD) of within-subject difference on the log scale is 0.35 for AUC(0-30min) and 0.25 for early 50% t_{max} , according to an analysis of internal Lilly data (CCI) for LY900014 and Humalog administered in a repeat-dose study.

With this sample size, there is approximately 80% power to detect a -30 mg·h/dL difference (LY900014 versus Humalog when both are given immediately before meals) in postprandial glucose Δ AUC[0-2h]. This is based on an analysis of ITRG which showed a SD of within-patient difference of 56.20 mg·h/dL on the original data scale.

Patients who are randomized but drop out before completing assigned treatment may be replaced to ensure that approximately 30 patients complete the study.

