8. DEFINITION OF ANALYSIS POPULATIONS

The “Safety” population will consist of all patients who received at least one dose of study drug, regardless of whether or not they completed all protocol requirements.

Primary statistical analyses of PK parameters will be conducted on the set of patients who have evaluable PK data from at least one period where LY900014 is dosed and at least one period where Humalog is dosed. The insulin lispro PK is not influenced by the injection-to-meal timing of dosing.

For the analyses of GD parameters, patients with evaluable GD data for both treatments (LY900014 and Humalog) within each injection-to-meal timing (immediately before the start of meal or 20 minutes after the start of the meal) will be included. If data for only one treatment (LY900014 or Humalog) exists for an injection-to-meal timing, that data will not be included in the analysis.

Supportive analyses will be conducted on the set of patients who complete all treatment periods. A completer is defined as a patient with data for all 4 combinations of treatment and injection-to-meal timing.

All protocol deviations that occur during the study will be considered for their severity/impact and will be taken into consideration when subjects are assigned to analysis populations.

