9.4.2 Glucodynamic Statistical Inference

Patients who did not complete the entire meal or had significant changes in nutrient consumption of the standardized liquid test meal or dose changes during the MMTTs across periods included in the statistical analysis will be excluded from all the statistical analyses of the GD parameters. Patients which don't have evaluable data for both treatments (Humalog and LY900014) for each injection-to-meal timing (immediately before the start of meal or 20 minutes after the start of the meal) will be excluded from the statistical analysis of the PD parameters.

Summary statistics (including number of patients, mean, SD or standard error, minimum, and maximum) will be presented by treatment and by timing of dose (all 4 combinations of treatment and timing of dose).

The GD parameters on the original scale (not log-transformed) will be analyzed using a statistical model that includes treatment, timing of dose (0 [immediately before the test meal], 20 minutes following the start of test meal), treatment-by-timing of dose interaction, and period as fixed effects and patient as a random effect. The p-value on the difference between LSmeans will be used to determine statistical significance and the corresponding 95% CIs for the LSmean ratios from Fieller's theorem will be presented.

Example SAS code:

```
proc mixed data=gd;
class patient period treatment timing;
model gd = treatment timing period treatment*timing / ddfm=kr
alpha=0.05;
random patient;
lsmeans treatment*timing;
run;
```

Statistical significance will be achieved when the p-value for a test is less than 0.05.

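### SAP 8 drops evaluable meal tests that the planned glucodynamic model could use, at a modest cost in precision, and SAP 8, 9.4.1 and 9.4.2 do not define one glucodynamic analysis set

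*SAP*

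**What the plan says.** - **SAP 8** admits GD data only where both products are evaluable at a given timing. Otherwise: "If data for only one treatment (LY900014 or Humalog) exists for an injection-to-meal timing, that data will not be included in the analysis". Its supportive set is completers, meaning patients with data in all four cells. For PK it asks for evaluable data from "at least one period where LY900014 is dosed and at least one period where Humalog is dosed".
- **SAP 9.4.1** places any patient with one dose and evaluable GD data in the GD analysis set. It also removes glucose values recorded after an intervention for hypo- or hyperglycemia.
- **SAP 9.4.2** restates the pairing rule with patients, not data, as what is excluded. The model has treatment, timing, "treatment-by-timing of dose interaction, and period as fixed effects and patient as a random effect", and the example code requests "lsmeans treatment*timing".
- **SAP 4.2** gives the secondary objective: "To evaluate the effect of injection-to-meal timings (immediately before the start of meal, and 20 minutes following the start of the meal". The sentence goes on to make this a matter of the GD response to LY900014 relative to Humalog.
- **SAP 7** plans up to 36 enrolled for about 30 completers. For LY900014 versus Humalog, both given immediately before the meal, "there is approximately 80% power to detect a -30 mg·h/dL difference" in ΔAUC(0-2h), from an "SD of within-patient difference of 56.20 mg·h/dL on the original data scale".
- **Protocol 10.3** makes completers the primary PK and GD set, with an optional supportive analysis of patients who complete at least one period. **SAP 11** reports no changes from the protocol's analyses.

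**The concern.** Take a patient with LY900014(0), Humalog(0) and LY900014(+20) but no Humalog(+20). The rule deletes the LY900014(+20) value. With it go two complete within-patient comparisons: LY900014(+20) with LY900014(0), and LY900014(+20) with Humalog(0). A patient with only LY900014(0) and LY900014(+20) contributes nothing, despite having a full timing pair. The model does not need same-timing pairs, and the SAP's supportive set is completers, so no planned SAP inference restores these values.

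The second problem is that the three SAP sections describe different datasets: every patient with evaluable GD data (9.4.1), data paired within timing (8), or, on one reading, only patients with all four cells (9.4.2). SAP 9.4.1 could be meant for parameter derivation only, but it does not say so. On the whole-patient reading the main set is in effect the completer set, and the supportive analysis would repeat the main one.

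At stake are some precision, mostly for contrasts across timings, and certainty about which patients enter the GD analysis.

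**Working it through.** **Inputs.** SD of the within-patient difference is 56.20 mg·h/dL and the difference of interest is 30 mg·h/dL, with two-sided alpha 0.05, 30 completers and 36 enrolled (SAP 7). Residual variance σ² = 56.20²/2 = 1579.2, so σ = 39.74. Not in the documents, so assumed: how many MMTTs are non-evaluable, the intraclass correlation (ICC, range 0.2-0.8), and the four sequences (averaged over all 24 orders).

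**1. The plan's own figure.** SE = 56.20/√30 = 10.26 and noncentrality = 30/10.26 = 2.92. Paired t power with 29 df is 80.7%. The stated 80% is reproduced.

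**2. What is deleted.** A patient with three evaluable MMTTs always loses exactly one. A patient with only the first two periods loses both in 16 of the 24 orders. If each MMTT is non-evaluable independently with probability p, the rule discards a fraction p of the evaluable ones.

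**3. Hand check.** Take 30 completers plus six patients with three MMTTs, balanced over which cell is missing. Use within-patient information only and ignore period.

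- *All evaluable data.* A completer carries information 1/4 on each pair of cells. A three-MMTT patient carries 1/3 on each of three of the six pairs, on average 1/6, or two thirds of a completer. The effective number is 30 + 6 × 2/3 = 34. Every pairwise contrast has variance 2σ²/34 = 92.9 (SE 9.64).
- *SAP 8, same-timing product contrast.* Each timing has 30 + 3 = 33 pairs: 2σ²/33 = 95.7 (SE 9.78). Ratio 34/33 = 1.03.
- *SAP 8, timing contrast.* LY(0) − LY(+20) is half the interaction plus half the sum of the two products' timing differences. The first part has variance σ²/33. The second is informed only by completers, σ²/30. The sum is 100.5 (SE 10.02). Ratio 100.5/92.9 = 1.08. LY900014(+20) versus Humalog(0) gives the same value.
- *Whole patient removed.* Only the 30 completers remain: 2σ²/30 = 105.3 (SE 10.26). Ratio 34/30 = 1.13, for every contrast.

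**4. Full model (generalized least squares with period effects and random patient, ICC 0.2-0.8).**

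| Scenario | Contrast | SE, all data | SE, SAP 8 | Extra variance |
|---|---|---|---|---|
| 30 complete, 6 lack one | timing; LY(+20) vs H(0) | 9.60-9.63 | 9.86-10.00 | 5.5-7.7% |
| 30 complete, 6 lack one | same-timing product | 9.60-9.63 | 9.78 | 3.1-3.9% |
| 30 complete, 6 lack one | interaction | 13.57-13.62 | 13.84 | 3.1-3.9% |
| 24 complete, 12 lack one | timing; LY(+20) vs H(0) | 9.85-9.92 | 10.44-10.80 | 12-19% |
| 24 complete, 12 lack one | same-timing product | 9.85-9.92 | 10.26 | 7-9% |

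With the whole patient removed in the first scenario: 10.26²/9.62² = 1.14, that is +14%.

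Taking 30 mg·h/dL as a yardstick, power by the normal approximation, Φ(30/SE − 1.96), for the timing contrasts falls from about 88% to 85-86% in the first scenario and from about 86% to 79-82% in the second.

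**5. Assumed rates per MMTT (30 patients, patient variance equal to residual variance).** At p = 5%, 10% and 15% the SE rises by 3.9%, 8.1% and 13.2% for timing contrasts, and by 2.1%, 4.3% and 6.9% for same-timing product contrasts. At 10% the variances rise by 1.081² − 1 = 17% and 1.043² − 1 = 9%.

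**The case against.** The strongest defense is that the rule fits the objective as worded. SAP 4.2 asks about LY900014 compared with Humalog, and the only powered GD contrast is the product comparison immediately before the meal. The rule keeps every same-timing product pair. No section names LY900014(+20) versus LY900014(0), or LY900014(+20) versus Humalog(0), as a test; Protocol 3.1 speaks of exploring the two timings. SAP 8 also keeps more data than the protocol's completers-only primary set. All of this stands, and it limits the point. It does not remove it, because the same-timing contrasts and the interaction also lose 3-4%.

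PK is no clean precedent for using every value. It too requires both products, and it pools timings because SAP 8 holds that timing does not influence insulin lispro PK.

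A reader might infer that pairing needs data missing completely at random, so that using all data is always safer. That does not follow. If missingness depends on the patient's own general level, the same-timing paired difference is still unbiased, because the level cancels. In simulations under assumed mechanisms of this kind, bias in the same-timing product contrast was about 0.4 mg·h/dL in size under the pair rule (Monte Carlo error 0.34 in one of them) and 1.2 to 2.5 with all data. For the timing contrasts it was about −2.5 under the pair rule and between −0.4 and 0.3 with all data. It is a trade-off, and a reason to keep the paired analysis as a sensitivity analysis.

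**Conclusion.** The point holds as a modest loss of precision plus an unclear analysis set. Under SAP 8 as worded, with 30 of 36 completing and six patients lacking one MMTT each, the extra variance is about 5-8% for contrasts across timings and 3-4% for same-timing product contrasts and the interaction. If the six drop out after one, two or three periods instead, the SE of the timing contrasts rises by about 2.5-2.9%. If SAP 9.4.2 removes the whole patient, the cost is about 14% for every contrast.

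A reader might infer a loss equal to 4 or 5 of 30 patients (30 − 30/1.17 = 4.4). That needs 10% of MMTTs to be non-evaluable among only 30 patients. The documents give no such rate, plan for up to 36 patients, and allow drop-outs to be replaced and each period to be rescheduled once. The exclusion of post-intervention glucose could raise the rate, but by how much cannot be known from the documents.

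All-data analysis was not less precise for any contrast examined. The case for change rests on that and on the need for one defined set, not on a general claim that the paired analysis is biased.

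**What to change.** 1. In SAP 8 and 9.4.2, fit the GD model to all evaluable MMTTs of patients with at least two, and show N per cell. A patient with one MMTT has no within-patient contrast to lose.
2. Keep two sensitivity analyses: the within-timing paired set, for its robustness in the same-timing product contrast, and the completer set.
3. Make SAP 8, 9.4.1 and 9.4.2 define one GD set, and state whether an exclusion removes the MMTT or the patient.
4. Record in SAP 11 the departure from the protocol's completers-only primary set.

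The cost is SAP wording and one further model run; no new data or procedures are needed. The downsides are that N differs slightly between cells and that a little between-patient information enters the product contrasts.

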9. STATISTICAL METHODOLOGY

9.1 General

Data listings will be provided for all data that is databased. Summary statistics and statistical analysis will only be presented for data where detailed in this SAP. For continuous data, summary statistics will include the arithmetic mean, arithmetic SD, median, min, max and N; for log-normal data (e.g. the PK parameters: AUCs and maximum observed drug concentration [C_{max}]) the geometric mean and geometric coefficient of variation (CV%) will also be presented. For categorical data, frequency count and percentages will be presented. Data listings will be provided for all subjects up to the point of withdrawal, with any subjects excluded from the relevant population highlighted. Summary statistics and statistical analyses will generally only be performed for subjects included in the relevant analysis population. For the calculation of summary statistics and statistical analysis, unrounded data will be used.

Mean change from baseline is the mean of all individual subjects' change from baseline values. Each individual change from baseline will be calculated by subtracting the individual subject's baseline value from the value at the sequential timepoints. The individual subject's change from baseline values will be used to calculate the mean change from baseline.

Data analysis will be performed using 

9.2 Demographics and Subject Disposition

Subject disposition will be listed. The demographic variables age, sex, race, ethnicity, country of enrolment, screening HbA1c, screening fasting blood glucose, screening fasting C-peptide, duration of T1DM, site ID, body weight, height, hip circumference, waist circumference and body mass index will be summarized and listed.

In addition, the following dosing data will be listed and summarized:

- Insulin dose at screening (stored in the concomitant dataset) for basal, bolus, and total.
- The average of days -3, -2 and -1 for Period 1 for basal insulin (glargine), bolus insulin (Humalog), and total daily insulin (Humalog and glargine).
- Dose finding dose for the MMTT (the dose administered for the dose finding and the dose selected after the dose finding on Day 1, Period 1 which will be used for all MMTT, and is the dose selected on the exposure dose finding page).

9.3 Pharmacokinetic Analyses

9.3.1 Pharmacokinetic Parameter Estimation

Patients who complete at least 1 MMTT and have measurable insulin lispro concentrations will be included in the analysis dataset for the PK analyses. PK analyses will be conducted using standard noncompartmental methods of analysis (CCI [REDACTED]) on a computer that meets or exceeds the minimum system requirements for these programs. It is possible that other validated equivalent PK software programs may be utilized if appropriate, warranted, and approved by global PK management. The version of any software used for the analysis will be documented, and the program will meet the Lilly requirements of software validation.

Free serum insulin lispro concentrations will be used to calculate several PK parameters, including time to early half-maximal drug concentration (early 50% t_{max}), time to late half-maximal drug concentration (late 50% t_{max}), maximum observed drug concentration (C_{max}), time to maximum observed drug concentration (t_{max}), AUC from time zero to time t , where t is the last time point with a measurable concentration [AUC(0- t_{last})], AUC from time 0 to 15 minutes [AUC(0-15min)], AUC from time 0 to 30 minutes [AUC(0-30min)], AUC from time zero to 1 hour [AUC(0-1h)], AUC from time zero to 7 hours [AUC(0-7h)], AUC from time 3 to 7 hours [AUC(3-7h)] and AUC from time zero to infinity [AUC(0- ∞)]. Other parameters may be calculated as deemed appropriate. Additional partial AUCs may be computed as necessary, such as AUC from time zero to 2 hours.

The insulin lispro PK parameters for assessing faster insulin lispro absorption are the early 50% t_{max} and AUC(0-30min).

The AUC(0- ∞) will be the key PK parameter for the statistical analysis of the total insulin lispro exposure.

Although attempts will be made to adhere to the scheduled collection times, it is recognized that situations arise that may compromise sample collection at the scheduled times. Parameters will be individually calculated for each patient based on actual collection times and presented by summary statistics.

9.3.2 Pharmacokinetic Statistical Inference

Patients who did not keep identical insulin lispro doses for both treatments (LY900014 and Humalog) will be excluded from the statistical analysis of the PK parameters.

Log-transformed AUCs and C_{max} for insulin lispro will be evaluated to estimate geometric means, ratios of geometric means of insulin lispro within LY900014 to Humalog, and their corresponding 95% CIs of the ratios using the mixed-effects model that includes treatment (LY900014, Humalog) and period as fixed effects and patient as a random effect.

Example SAS code:

```
proc mixed data=pk;  
class patient period treatment;
```

```
model logpk = treatment period / ddfm=kr alpha=0.05;  
random patient;  
lsmeans treatment;  
run;
```

For AUC(0-∞), the analysis above will be used to produce an assessment of within-patient and between-patient variability for each treatment.

The same model without log transformation will be used for the analysis of the PK time parameters (early 50% t_{max} , late 50% t_{max} , and t_{max}). Least-squares means (LSmeans), treatment differences in LSmeans, and the corresponding 95% CIs for the treatment differences will be estimated from the model. The p-value on the difference between LSmeans will be used to determine statistical significance. The treatment ratios and 95% CIs for the ratios will be calculated using Fieller's theorem (Chow and Liu 2009).

Statistical significance will be achieved when the p-value for a test is less than 0.05.

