10.3.2.2. Pharmacokinetic Statistical Inference

Patients who did not keep identical insulin lispro doses for the MMTTs across all periods will be excluded from the statistical analysis of the PK parameters.

Log-transformed AUCs, C_{max} , CL/F and Vz/F for insulin lispro will be evaluated to estimate geometric means, ratios of geometric means of insulin lispro within LY900014 to Humalog, and their corresponding 95% CIs of the ratios using the mixed-effects model that includes treatment (LY900014, Humalog) and period as fixed effects and patient as a random effect.

The same model without log transformation will be used for the analysis of the PK time parameters (early 50% t_{max} , late 50% t_{max} , t_{max} , and $t_{1/2}$). Least-squares means (LSmeans), treatment differences in LSmeans, and the corresponding 95% CIs for the treatment differences will be estimated from the model. The p-value on the difference between least squares (LS) means will be used to determine statistical significance. The treatment ratios and 95% CIs for the ratios will be calculated using Fieller's theorem (Chow and Liu 2009).

Statistical significance will be achieved when the p-value for a test is less than 0.05.

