5. STUDY DESIGN

This is a Phase 1, patient- and investigator-blind, randomized, 2-treatment, 4-period crossover study in patients with T1DM to evaluate the insulin lispro PK and GD characteristics of LY900014 compared to Humalog following single SC injections administered at 2 different injection-to-mealtime intervals; either immediately before or 20 minutes following the start of the test meal. This study may be conducted at 1 or more clinical research units (CRUs).

Treatment	LY900014 or Humalog	Dose Timing Relative to Meal (minute)*
A	LY900014	0
B	LY900014	+20
C	Humalog	0
D	Humalog	+20

* Time 0 is immediately before test meal

Abbreviations: ED = early discontinuation; T1DM = type 1 diabetes mellitus

Figure 1. Illustration of study design

Patients will be required to attend the CRU on at least 8 occasions (no more than 10 occasions if dose-finding and/or one MMTT rescheduled) as noted in the Study Schedule (see Section 2 of protocol):

- Informed consent
- Screening visit
- Lead-in and insulin transition period (see Section 9.2.1 of the protocol)
- 4 inpatient CRU study visits (including dose finding assessment [see Section 9.2.2 of the protocol])
- A follow-up visit

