Eligible patients who have satisfied the entry criteria and completed all screening procedures will return to the CRU at least 2 weeks prior to Period 1 Day -2 to begin a lead-in and insulin transition period. When patients visit the CRU to begin the lead-in period, patients will receive instruction on general diabetes education including measurement of self-monitored plasma glucose (SMPG) and receive instruction on the insulin transition (see Section 9.2.1 of the protocol). During the insulin transition period, patients will transition from their current basal insulin therapy to site provided insulin glargine and Humalog CCI (see Section 9.2.1 of the protocol). Following insulin transition, patients will return to the CRU for the dose-finding assessment (see Section 9.2.2 of the protocol) on either the evening of Day -2, Period 1 or early morning of Day -1, Period 1. The dose-finding assessment will use Humalog administered immediately before a standardized liquid test meal to inform the dose of LY900014 and Humalog to be used during subsequent study MMTT assessments. Upon completion of the dose-finding assessment, patients will be randomised to 1 of 4 treatment sequences. Prior to the MMTT in each study period, patients will undergo a run-in period (see Section 9.2.3.1 of the protocol) to achieve a predetermined glucose target of 135 ± 15 mg/dL (7.5 ± 0.8 mmol/L). Once the glucose target has been attained, patients will proceed with the MMTT in which a single individualized SC dose of LY900014 or Humalog will be administered either immediately before the test meal or 20 minutes following the start of the test meal (see Section 9.2.3.2 of the protocol).

Doses of LY900014 and Humalog during the 4 study periods will be separated by a minimum washout of approximately 21 hours. The maximum duration allowed for all 4 periods is approximately 6 weeks. Patients will continue using site-provided Humalog and insulin glargine during the washout periods between MMTTs (see Section 7.7 for use of concomitant medication and basal insulin). During the washout periods, patients will be instructed to perform regular blood glucose monitoring (see Section 9.5.7 of the protocol).

Following completion of all study procedures in each Period, patients may be offered a meal and discharged from the CRU at the discretion of the principal investigator.

Study governance considerations are described in detail in Appendix 3 of the protocol.

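### SAP 9.3.2 promises within- and between-patient variability of AUC(0-∞) for each treatment, but the model it names yields only one pooled pair for both products

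*SAP*

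**What the plan says.** SAP section 9.3.2 analyses the log-transformed AUCs and Cmax with "treatment (LY900014, Humalog) and period as fixed effects and patient as a random effect". The example SAS code has the same structure. Treatment enters only the mean, through "model logpk = treatment period / ddfm=kr alpha=0.05", and the only covariance statement is "random patient". There is no grouping option, no random treatment effect within patient and no repeated statement.

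The sentence after the code states that, for AUC(0-∞), "the analysis above will be used to produce an assessment of within-patient and between-patient variability for each treatment". AUC(0-∞) is the only parameter given this promise. SAP section 9.3.1 makes it the key parameter for total exposure.

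Protocol section 10.3.2.2 specifies the same "mixed-effects model that includes treatment (LY900014, Humalog) and period as fixed effects and patient as a random effect" and does not mention variability by treatment. The geometric CV% in SAP section 9.1 does not separate within-patient from between-patient variation.

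**The concern.** Output for each treatment needs a within-patient and a between-patient variance for LY900014 and another two for Humalog. A model in which treatment affects only the mean assumes that the two products share both variances, so it cannot show a difference between them.

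A programmer who follows the text literally has one pair of numbers for a two-row table. If that pair were entered in both rows, the table would show equal variability because the model assumed it, whatever the data showed. Another programmer might fit each product separately and produce a different table from the same SAP. SAP section 3 requires sign-off before first dosing and makes the SAP and table shells the template for the study report, so the text is worth settling in advance.

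**Working it through.** The plan gives no figure for AUC(0-∞) variability, so there is nothing to reproduce. The check is a parameter count, followed by a calculation under assumed SDs.

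**Inputs from the documents.** Two products, four periods and two dose timings, so each completer receives each product twice (SAP section 5); 30 completers (SAP section 7); the model in SAP section 9.3.2. The text available does not list the four sequences, so three sets were assumed: ABDC/BCAD/CDBA/DACB, ABCD/BCDA/CDAB/DABC and ABCD/BADC/CDAB/DCBA.

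**Step 1: count.** The model is log AUC = treatment + period + patient effect + residual. Its covariance parameters are one patient variance and one residual variance, 2 in all. The promised output needs 2 products × 2 components = 4.

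**Step 2: can the design supply four?** Yes. Two doses of each product per completer separate within from between variation for each product. The gap is in the specification, not the design.

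**Step 3: what the stated model returns.** Let w_L and w_H be the true within-patient SDs, b_L and b_H the between-patient SDs, and ρ the correlation of a patient's two product effects. Each completer gives three within-patient contrasts:

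- two within product, with expected squares w_L² and w_H²;
- one between products, with expected square D + (w_L² + w_H²)/2, where D = b_L² + b_H² − 2ρ·b_L·b_H.

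Their average gives

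pooled within-patient variance ≈ (w_L² + w_H²)/2 + D/3.

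Example: w = 0.15 and 0.30, b = 0.25 and 0.35.

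- First term: (0.0225 + 0.0900)/2 = 0.05625.
- ρ = 1: D = 0.0625 + 0.1225 − 0.1750 = 0.0100. Variance 0.05625 + 0.00333 = 0.05958; SD 0.244.
- ρ = 0.5: D = 0.0625 + 0.1225 − 0.0875 = 0.0975. Variance 0.05625 + 0.03250 = 0.08875; SD 0.298.

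The table uses exact expected mean squares on 120 − 30 − 3 − 1 = 86 residual df (observations less patients, periods and treatment). The three sequence sets agree to within 0.001. All SDs are assumptions.

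| Within SDs | Between SDs | ρ | Pooled within | Ratio to smaller; larger | Pooled between |
|---|---|---|---|---|---|
| 0.20, 0.20 | 0.30, 0.30 | 1.0 | 0.200 | 1.00; 1.00 | 0.300 |
| 0.20, 0.20 | 0.30, 0.30 | 0.9 | 0.214 | 1.07; 1.07 | 0.290 |
| 0.20, 0.20 | 0.30, 0.30 | 0.7 | 0.240 | 1.20; 1.20 | 0.269 |
| 0.18, 0.22 | 0.30, 0.30 | 1.0 | 0.201 | 1.12; 0.91 | 0.300 |
| 0.18, 0.22 | 0.30, 0.30 | 0.9 | 0.215 | 1.19; 0.98 | 0.290 |
| 0.15, 0.30 | 0.25, 0.35 | 1.0 | 0.244 | 1.63; 0.81 | 0.299 |
| 0.15, 0.30 | 0.25, 0.35 | 0.9 | 0.255 | 1.70; 0.85 | 0.289 |
| 0.15, 0.30 | 0.25, 0.35 | 0.5 | 0.297 | 1.98; 0.99 | 0.245 |

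In the first block the products have equal variances, so all of the distortion there comes from patient-by-treatment variation.

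A simulation of 4,000 trials on the first sequence set gave pooled within-patient SDs of 0.244 and 0.297 for the last scenario at ρ = 1.0 and 0.5. Separate fits by product averaged 0.150 and 0.300 at ρ = 1.0.

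**Step 4: precision of separate fits.** One product has 60 observations. Less 30 patients and 3 period terms, that leaves 27 residual df. It is 28 under the third sequence set, where one period contrast is absorbed by the patient effects. The 95% CI factors for an SD are √(df/χ²) at the 0.975 and 0.025 quantiles: 0.79 to 1.36 at 27 df and 0.79 to 1.35 at 28 df.

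SAP section 8 admits patients with "evaluable PK data from at least one period where LY900014 is dosed and at least one period where Humalog is dosed". A patient with a single period of a product adds no within-patient information for it. If 3 or 6 of 30 were in that position, 27 df would fall to 24 or 21, and the interval would widen to about 0.78 to 1.39 or 0.77 to 1.43.

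**The case against.** The strongest reply is that the intent is plain. The code is labelled an example, and a programmer would probably run the random-patient model separately by product. SAP section 3 also places the detailed output descriptions in a table-shell document that is not available here, and it may already settle the matter. Identical rows in a table would be noticed at review.

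Much of this stands as to harm. Identical values in the report are a possibility, not a prediction. It does not rescue the text: the model in words has the same structure as the code, and in a fit by product the treatment term drops out, so it is no longer the analysis described above it.

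The size is also open to challenge. Every SD is assumed. With a modest contrast (0.18 and 0.22, correlation 1) the pooled 0.201 lies well inside the sampling error of either product's own estimate.

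A reader might infer that the variability model must also include dose timing. The documents do not require it: SAP section 8 states that timing does not influence insulin lispro PK, and the PK model omits it. Adding it is a choice that costs 1 df per product in the separate fits.

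**Conclusion.** The sentence is wrong as written. The named model has two covariance parameters shared by both products and cannot give AUC(0-∞) variability by treatment, and nothing else in the protocol or SAP text supplies a structure that can. This follows from the parameter count and needs no assumption.

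The numerical consequence is unknown. It ranges from none, when the variances are equal and patient effects correlate at 1, to the pooled 0.244 to 0.297 found for the largest assumed contrast. Those figures rest on 30 completers and on assumed SDs and sequences.

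A reader might infer that the primary PK comparison is compromised. The documents do not support that. The primary endpoints are early 50% tmax and AUC(0-30min). The power statements rest on SDs of within-patient differences for those two and for glucose ΔAUC(0-2h), and nothing in the plan uses the AUC(0-∞) variability output. This is a low-priority text correction.

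**What to change.** For AUC(0-∞) variability only, replace the reference to the analysis above with a named model:

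- Keep the SAP's fixed effects, treatment and period.
- Use treatment-specific covariance: `random treatment / subject=patient type=fa0(2);` (or `type=csh`) with `repeated / subject=patient group=treatment;`.
- Prespecify the fallback if this does not converge: the random-patient model with period, fitted separately by treatment. Timing may be added to it.
- Report each treatment's within- and between-patient variances with confidence intervals, and the number of patients who contribute two periods of that product.

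If only pooled values are intended, delete the three words that promise the result by treatment. Either change removes the contradiction. The model for means and ratios stays as it is.

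The cost is a few lines of SAP text and code, with no change to design, data collection or sample size. The drawbacks are possible non-convergence of the richer covariance and imprecise per-treatment estimates, as shown in step 4.
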